10.3 Reporting of Serious Adverse Events and Unanticipated Problems

When an adverse event has been identified, the study team will take appropriated action necessary to protect the study participant and then complete the Study Adverse Event Worksheet and log. The sponsor-investigator will evaluate the event and determine the necessary follow-up and reporting required.

Serious Adverse Events will be reported as part of regular adverse event reporting mechanisms via the data capture system and logged for review reporting.

10.3.1 Investigator Reporting: Notifying the Mayo IRB:

The IRB requirements reflect the guidance documents released by the Office of Human Research Protections (OHRP), and the Food and Drug Administration (FDA) in early 2007 and are respectively entitled “Guidance on Reviewing and Reporting Unanticipated Problems Involving Risks to Subjects or Others and Adverse Events” and “Guidance for Clinical Investigators, Sponsors, and IRBs: Adverse Event Reporting – Improving Human Subject Protection.”

10.3.1.1 According to Mayo IRB Policy any serious adverse event (SAE) which the Principal Investigator has determined to

be a UPIRTSO must be reported to the Mayo IRB as soon as possible but no later than 5 working days after the investigator first learns of the problem/event.

10.3.1.2

Non-UPIRTSO – the investigator reports problems or events that do NOT meet criteria of an UPIRTSO in summary format at the time of the next continuing review. The investigator monitors the severity and frequency of subsequent nonUPIRTSOs.

Consider the following information to collect when developing any forms for documentation of adverse events.

Example

Information collected on the adverse event worksheet (and entered in the research database):

- Subject's name:
- Medical record number:
- Disease/histology (if applicable):
- The date the adverse event occurred:
- Description of the adverse event:
- Relationship of the adverse event to the research (drug, procedure, or intervention):
- If the adverse event was expected:
- The severity of the adverse event: (use a table to define severity scale 1-5)
- If any intervention was necessary:
- Resolution: (was the incident resolved spontaneously, or after discontinuing treatment?)
- Date of Resolution:

The investigator will review all adverse event reports to determine if specific reports need to be made to the IRB and FDA. The investigator will sign and date the adverse event report when it is reviewed. For this protocol, only directly related SAEs/UPIRTSOs will be reported to the IRB.

10.4 CTCAE v4.0 is used for the following AEs to be graded at each evaluation and pretreatment symptoms/conditions to be evaluated at baseline:

System Organic Class	Adverse events/Symptoms
Gastrointestinal	Diarrhea
	Fecal incontinence
	Proctitis
	Rectal hemorrhage
	Rectal ulcer
	Small intestinal obstruction

	Stricture/Stenosis: Rectum
Renal/Genitourinary	Bladder spasm
	Hematuria
	Urinary frequency
	Urinary incontinence
	Urinary tract obstruction
	Urinary tract pain
	Urinary urgency
	Cystitis noninfective
	Urinary retention
Sexual/Reproductive function	Erectile dysfunction

Acute AEs are defined as those that occur from day 1, or commencement of radiation therapy, through 3 months after the completion of protocol treatment.

All AEs seen after 3 months after the completion of protocol treatment are considered late effects.

10.4.1 Submit via appropriate reporting mechanisms (i.e., paper or electronic) the following AEs experienced by a patient and not specified in Section 10.4:

Grade 5 AEs (Death)

10.4.1.1.1 Any death within 30 days of the patient's last study treatment or procedure regardless of attribution to radiation treatment

10.4.1.1.2 Any death more than 30 days after the patient's last study treatment or procedure that is felt to be at least possibly related to radiation treatment must also be submitted as a Grade 5 AE, with a CTCAE type and attribution assigned.

10.5 Monitoring and Auditing

The investigator will permit study-related monitoring, audits, and inspections by the IRB, the sponsor, and government regulatory agencies, of all study related documents (e.g. source documents, regulatory documents, data collection instruments, study data etc.). The investigator will ensure the capability for inspections of applicable study-related facilities (e.g. pharmacy, diagnostic laboratory, etc.).

Participation as an investigator in this study implies acceptance of potential inspection by government regulatory authorities and applicable compliance offices

10.5.1 Medical Monitoring

It is the responsibility of the Principal Investigator to oversee the safety of the study at his site. This safety monitoring will include careful

assessment and appropriate reporting of adverse events as noted above, as well as the construction and implementation of a site data and safety-monitoring plan. Medical monitoring will include a regular assessment of the number and type of serious adverse events. Any serious adverse events will be followed up by the sentinel event reporting procedure.

10.5.2 Internal Data and Safety Monitoring Board

As an interventional study, this study will be reviewed in conjunction with the Mayo Clinic Cancer Center DSMB processes. The study will also be reviewed by the Radiation Oncology Research Executive Board on a yearly basis to assess accrual, adverse events, and any endpoint problems. Any safety issues requiring protocol changes will be communicated through protocol amendments.

The trial will be reviewed by the Cancer Center Auditing area on a bi-annual or yearly basis, dependent on random study selection. Accrual, adverse events, and any endpoint problems will be assessed. Any safety issues requiring protocol changes will be communicated through protocol amendments.

11.0 Treatment Evaluation

- 11.1 No evidence of disease: No clinical evidence of tumor recurrence including the freedom from biochemical (PSA) failure (Section 11.2.2.1)
- 11.2. Recurrence of disease: The site of recurrence will be collected, and classified as biochemical failure, local recurrence, regional recurrence and/or distant recurrence.
 - 11.2.1 Biochemical (PSA) failure: PSA nadir is defined as the lowest PSA value reached after completion of treatment. Biochemical failure is defined as a PSA value that is \geq PSA nadir + 2.0 ng/mL with the date of biochemical failure set at the date of the PSA value that meets this criterion.
 - 11.2.2 Local recurrence: Local recurrence is defined when one or more of the followings occur: (1) ureteric obstruction at the level of the ureterovesical junction; urethral obstruction that requires prostatic resection (with resected tissue demonstrating prostatic adenocarcinoma) or urinary diversion; or hematuria due to prostate cancer progression, (2) positive prostate biopsy at \geq 24 months from the completion of protocol treatment (3) \geq 20% increase in the longest diameter of a target lesion in the prostate gland (for patients with a measurable target lesion at baseline), or a new lesion measuring \geq 1 cm short axis during follow-up (for patients with non-measurable lesion at baseline) in the setting of biochemical failure

11.2.3 Regional recurrence: Development of nodal metastasis in the pelvis which is defined as a new regional pelvic node that was normal at baseline (< 1.0 cm short axis) and increased to \geq 1.0 cm short axis during follow-up. Confirmation by biopsy is encouraged.

11.2.4 Distant recurrence: Development of nodal metastasis outside the pelvis, or a hematogenous (e.g., osseous, hepatic, etc.) lesion. Confirmation by biopsy is encouraged.

11.2.5 Disease-free survival: Disease-free survival duration will be measured from the date of registration to the date of biochemical, local, regional, or distant recurrence or the date of death from any cause.

11.2.6 Disease-specific survival: Disease-specific survival duration will be measured from the date of registration to the date of death due to prostate cancer. Death due to prostate cancer will be defined as:

11.2.6.1 Death attributed to carcinoma of the prostate by the investigator, or

11.2.6.2 Death due to complications of treatment

11.2.7 Overall survival: Survival duration will be measured from the date of registration to the date of death from any cause.

12.0 Descriptive Factors

12.1. Clinical tumor (T) classification: \leq T2 vs. \geq T3

12.2. Histologic grade: Gleason score \leq 7 vs. \geq 8

12.3. Pre-treatment serum PSA value: \leq 20 ng/mL vs. >20 ng/mL

This is the PSA value obtained most immediately before the start of neoadjuvant androgen deprivation therapy (see Section 7.2).

12.4. Patient age: \leq 70 years vs. >70 years.

13.0 Treatment/Follow-up Decision at Evaluation of Patient

Follow-up data will be collected and entered in accordance to Section 4.0. No follow-up data is required beyond 5 years from the date of study enrolment.

13.1 If a patient fails to complete the entire course of treatment for reasons other than toxicity or prostate cancer progression, he will be regarded as *inevaluable* and will be replaced. Baseline characteristics will be collected in the database. However, no further data collection will be collected.

13.2 A patient is deemed *ineligible* if after registration, it is determined that at the time of registration, he did not satisfy each and every eligibility criteria for study entry.

The patient may continue treatment off-protocol at the discretion of the physician as long as there are no safety concerns, and the patient was properly registered.

If the patient received treatment, all data up until the point of confirmation of ineligibility must be submitted, and collection of follow-up data will continue in accordance to Section 4.0. Event monitoring will be required per Section 18.0 of the protocol.

- 13.3 A patient is deemed a *cancel* if he is removed from the study for any reason before any study treatment is given. On-study material and the End of Active Treatment/Cancel Notification Form must be submitted. No further data submission is necessary.
- 13.4 A patient is deemed a *major violation*, if protocol requirements regarding treatment are severely violated such that evaluability for primary end point is questionable. All data up until the point of confirmation of a major violation must be submitted. The patient will continue the active monitoring phase and the event-monitoring phase of the study. The patient may continue treatment off-protocol at the discretion of the physician as long as there are no safety concerns, and the patient was properly registered.
- 13.5 When the patient develops a biochemical recurrence only, he will continue on the protocol test schedule until further medical management is implemented at the discretion of his physician.
- 13.6 When the patient develops a local, regional, or distant recurrence, he will go off study with no further scheduled follow-up tests.

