4.0 Test Schedule

Tests and procedures	Active Monitoring Phase					Event Monitoring Phase
	≤ 120 days prior to registration	Within 2 weeks prior to RT	During RT (weekly)	End of RT (+/- 5 days)	Post-RT month ³ : 3, 6, 12, 18, and 24	
History, Physical exam, ECOG	X				X	X ⁷
PSA	X				X	X
Serum total testosterone	X				X ²	X ²
CBC, AST, ALP, Total Bilirubin, Creatinine	X				X ⁴	X ⁴
Path review ¹	X					
CT scan of abdomen and pelvis, or MRI of pelvis	X				X ⁴	X ⁴
Bone scan	X				X ⁴	X ⁴
GI and GU toxicity assessment (CTCAE v4.0)		X	X	X	X	X
Questionnaires ⁵	X ⁶			X	X	X

1. Optional; For outside prostate biopsy only
2. Serum total testosterone: to be performed post-RT month 12, 24, 36, 48, and 60
3. Month: targeted month +/- 1 month
4. Only when relapse occurs
5. Questionnaires [including Patient-Reported Outcomes version of the CTCAE, EPIC-26, American Urologic Association Symptom Index score (*paper*), and International Index of Erectile Function – Erectile Function Domain (*paper*)], which are currently parts of a routine clinical practice, will be administered electronically to patient in conjunction with the Registry and IRB# 15-000136.

6. Baseline questionnaires should be completed prior to patient starting hormone therapy if possible.
7. Only at 36, 48, and 60 months

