16.3 Analysis Plan

16.3.1 Primary Outcome Analyses:

16.3.1.1 Definition: The primary endpoint of this trial is the proportion of patients who experience a late grade 3 or higher GI or GU toxicity. Toxicity will be defined as an adverse event possibly, probably, or definitely related to proton beam therapy. A late GI or GU toxicity will be defined as a GI or GU toxicity that occurs between 3 months and 2 years from the completion of proton beam therapy. All patients meeting the eligibility criteria who have signed a consent form and have begun treatment will be evaluable for late toxicity, with the exception of patients determined to be a major violation.

16.3.1.2 Estimation: The proportion of grade 3 or higher GI or GU toxicities will be estimated by the number of patients with a late grade 3 or higher GI or GU toxicity divided by the total number of evaluable patients. Exact binomial 95% confidence intervals for the toxicity proportion will be calculated.

16.3.2 Secondary Outcome Analyses:

16.3.2.1 Disease-free survival is defined as the time from registration until the time of the first occurrence of biochemical failure (Section 11.2.1), local recurrence, regional recurrence, distant metastases, or death due to any cause. The distribution of disease-free survival will be estimated using the method of Kaplan-Meier. The disease-free survival rate will be estimated at 2 years and 5 years.

16.3.2.2 Disease-specific survival is defined as the time from registration until the date of death due to prostate cancer (Section 11.2.6). The distribution of disease-specific survival will be estimated using the method of Kaplan-Meier. The disease-specific survival rate will be estimated at 2 years and 5 years.

16.3.2.3 Overall survival is defined as the time from registration until the death due to any cause (Section 11.2.7). The distribution of overall survival will be estimated using the method of Kaplan-Meier. The overall survival rate will be estimated at 2 years and 5 years.

16.3.2.4 An acute adverse event is defined as an adverse event that occurs any time between registration and 3 months after the completion of proton beam therapy. The rate of \geq grade 3 GI or GU acute adverse events will be estimated by the number of patients with a \geq grade 3 GI or GU acute adverse event divided by the total number of evaluable patients. Exact binomial 95% confidence intervals for the true rate of \geq grade 3 GI or GU acute adverse events will be calculated.

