18.0 Records and Data Collection Procedures

18.1 Submission Timetable

Initial Material(s)

CRF	Baseline (Compliance with Test Schedule Section 4.0)
Demographics	
Patient Eligibility	
On-Study	≤2 weeks after registration
Adverse Events-Baseline	
PSA and Testosterone Values	
Prostate Radiotherapy Questionnaires	*6 months from accrual
Androgen Deprivation Treatment	

Test Schedule Material(s)

CRF	Active-Monitoring Phase ² (Compliance with Test Schedule Section 4.0)	Event-Monitoring Phase ³ (Compliance with Test Schedule Section 4.0)

	On-Study	At each evaluation during treatment	At end of treatment	Post-RT: 3, 6, 12, 18, and 24 months (Active Monitoring)	Post-RT: 30, 36, 42, 48, and 60 months (Event Monitor)
Adverse Event: Solicited Form	X	X	X	X	X
Adverse Events Other	X	X ¹	X ¹	X ¹	X ¹
Radiation Treatment			X		
Androgen Deprivation Treatment	X	X ⁴	X ⁴	X ⁴	X ⁴
End of Active Treatment			X		
PSA and Testosterone Values		X		X ⁵	X ⁵
Adverse Events: Post Radiation Treatment				X	X
Post Radiation Patient Status/Assessment				X	X ⁶
Prostate Radiotherapy Questionnaires				X	X
Consent Withdrawal form		X ¹	X ¹	X ¹	X ¹
Lost to Follow-up		X ¹	X ¹	X ¹	X ¹

1. When applicable
2. Post RT (Active monitoring phase): 3 months (+/- 1 months), 6 months (+/- 1 months), 12 months (+/- 1 months), 18 months (+/- 1 months), and 24 months (+/- 1 months) post RT.
3. Post RT (Event-monitoring phase): 30 months (+/- 1 months), 36 months (+/- 1 months), 42 months (+/- 1 months), 48 months (+/- 1 months), 54 months (+/- 1 months), and 60 months (+/- 1 months) post RT.
4. Coordinator will look to see if patient received Androgen Deprivation Therapy since the previous reporting period. If there was no change, indicate on form.
5. Testosterone is collected at post-RT month 12, 24, 36, 48, and 60 months post RT. However, if one was completed it should be entered into the CRF. Therefore, the form will populate at each visit, and if it wasn't completed because it was not required, indicate "not completed" on form.
6. History, physical exam, and ECOG are not required during Event Monitoring Phase.

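### Section 13.0 makes the 60-month post-RT visit non-required, so no required contact falls at or after the 5-year survival landmark

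*Combined protocol and SAP*

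**What the plan says.** Section 13.0 makes two statements in succession. First: "Follow-up data will be collected and entered in accordance to Section 4.0". Then: "No follow-up data is required beyond 5 years from the date of study enrolment".

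Section 4.0 places assessments at 60 months. History, examination and performance status in the event-monitoring phase are marked "Only at 36, 48, and 60 months", and testosterone is "to be performed post-RT month 12, 24, 36, 48, and 60". The visit window is "targeted month +/- 1 month".

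Section 18.1 sets the form timetable, which includes PSA. Its event-monitoring column is headed "Post-RT: 30, 36, 42, 48, and 60 months (Event Monitor", with no month 54. Footnote 3 to the same table ends its list with "54 months (+/- 1 months), and 60 months (+/- 1 months) post RT". Footnote 6 disagrees with Section 4.0 on whether an examination belongs to this phase, but both sections put an assessment at month 60.

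Sections 11.2.5 to 11.2.7 and 16.3.2 time disease-free survival (DFS), disease-specific survival (DSS) and overall survival (OS) from registration. All three are estimated by Kaplan-Meier at the same two landmarks; for DFS the text reads "The disease-free survival rate will be estimated at 2 years and 5 years". Section 2.2 names the three 5-year outcomes as secondary goals.

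**The concern.** Two clocks are in use. The cut-off and the survival endpoints start at enrolment or registration, and the visits start at the end of RT. A visit 60 months after RT must therefore come later than 60 months after enrolment, by the time taken to start and complete treatment. If that exceeds the one-month window, no 60-month visit can fall inside the required period, and Section 13.0 releases staff from a visit that Sections 4.0 and 18.1 schedule.

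The three 5-year survival estimates are at stake. A Kaplan-Meier estimate at 60 months needs men known to be event-free up to that time. If the last required contact comes months earlier, the final stretch has no scheduled ascertainment of deaths or clinical recurrences, and the reported 5-year value describes an earlier time. The month-54 discrepancy in 18.1 decides how much earlier.

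**Working it through.** **Inputs**
- Cut-off: 60 months from enrolment (13.0). Enrolment and registration are taken as the same date.
- Enrolment to start of treatment: 0 to 1 month (exclusion 3.2.8).
- RT course: 25 fractions, 5 per week (7.1.2).
- Window: plus or minus 1 month (4.0 footnote 3; 18.1 footnotes 2 and 3).
- Post-RT months are counted from the last fraction. This fits Section 16.1.1, which times late toxicity from completion of proton therapy.

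**The plan's own figure.** 25 / 5 = 5 weeks, as Section 1.4 states. From first to last fraction this is 32 days for a Monday start and up to 34 days for other weekday starts.

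**Bounds by hand.** Months from enrolment to the 60-month target = 60 + (delay to start + RT days) / 30.44.
- Earliest: 60 + 32/30.44 = 61.05 months. Taking off the one-month window gives 60.05, still after the cut-off.
- Latest: 60 + (31 + 34)/30.44 = 62.14 months.

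**Calendar check.** Months differ in length and the earliest margin is small. The dates were therefore enumerated for every enrolment day over four years and every weekday start from 0 to 1 month later, with 25 weekday fractions and no breaks.

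| Post-RT visit | Target relative to cut-off | Target, months from registration | Window edges, months from registration |
|---|---|---|---|
| 48 | 334 to 300 days before | 49.0 to 50.1 | 48.0 to 51.2 |
| 54 | 152 to 116 days before | 55.0 to 56.2 | 54.0 to 57.2 |
| 60 | 31 to 66 days after | 61.0 to 62.2 | 60.03 to 63.2 |

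The early edge of the 60-month window falls 1 to 37 days after the cut-off. No combination puts the visit on or before it.

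**Gap before the 5-year landmark if 13.0 governs**
- Last contact at month 54 (footnote 3): 116/30.44 = 3.8 to 152/30.44 = 5.0 months.
- Last contact at month 48 (column heading): 300/30.44 = 9.9 to 334/30.44 = 11.0 months.

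**Effect on the estimate.** If each man without an event is censored at his last required contact, the risk set is empty by 57.2 months at the latest (51.2 months under the column heading). The curve has no information after that, so its value at 60 months is the earlier value carried forward.

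**What a required 60-month visit changes.** Men seen there are known to be alive beyond 60 months from registration and are in the risk set at the landmark. Deaths and clinical recurrences diagnosed in the gap are recorded with their own dates. PSA failures behave differently. Section 11.2.1 dates them at the PSA that meets the criterion. One first found at the 60-month visit is dated after 60 months and cannot lower the 5-year DFS estimate.

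**The case against.** The strongest reply is that this is a clerical mismatch with little consequence. Several parts of it stand.

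- *Section 13.0 does not stop follow-up.* It says data are not required past 5 years. It forbids nothing, and its preceding sentence defers to Section 4.0. A reader might infer that follow-up ends at 5 years, or that no observation is scheduled there at all. The documents do not support either reading: a 60-month visit is scheduled in both 4.0 and 18.1. The defect is that 13.0 makes it non-required.
- *OS and DSS need vital status, not a clinic PSA.* The required period reaches 60 months from registration, so deaths known by then count. This stands. However, no contact is tied to that date, so knowing vital status depends on information arriving unprompted.
- *Censoring at last contact is not written in the plan.* True. The empty risk set is conditional on it.
- *The DFS bias is not cured.* A reader might estimate it from the cited 83.7% 5-year PSA relapse-free rate. At a constant hazard, -ln(0.837)/5 = 0.0356 per year, 3 to 12 unobserved months correspond to about 0.8 to 3.0 points, and one might credit the fix with removing that. The dating rule rules this out, since those failures stay uncounted at 5 years under either wording. The rate is also for PSA relapse alone, whereas DFS includes death and clinical recurrence. The figure is not a benefit of the fix.
- *The margin is thin.* In the earliest case it is one day. Counted from RT start, the early window edge would fall 0 to 31 days before the cut-off or on it, so some visits could qualify. The target date would still be at or after the cut-off.
- *Footnote 3 lists month 54.* It does, so month 54 is the better-supported reading. The column heading still contradicts it.

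**Conclusion.** The conflict between 13.0 and Sections 4.0 and 18.1 is real. Counting from the last fraction, every 60-month post-RT visit falls after the required period, 1.0 to 2.2 months late at its target date. The last required contact precedes the 5-year landmark by about 4 to 5 months under footnote 3, or 10 to 11 months under the column heading. If 13.0 is followed and men are censored at last contact, nobody is at risk at 60 months. The 5-year OS, DSS and DFS values are then earlier values carried forward, with no scheduled ascertainment of deaths and clinical recurrences in the gap.

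This rests on months counted from the last fraction, a start within one month of enrolment, and no treatment breaks. Breaks or later starts push the 60-month visit further past the cut-off. If the one-month limit in 3.2.8 refers to androgen deprivation, which 7.2 says usually begins 2 months before protons, all visits move about 2 months later: month 60 falls further outside and month 54 comes nearer the landmark.

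Only secondary, descriptive estimates are affected. The decision rule of Section 16.2.1, on toxicity up to 2 years in 51 men, is untouched. No size of DFS bias is claimed.

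**What to change.** Reconcile the sections with two wording changes:

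1. In Section 13.0, replace the cut-off at 5 years from enrolment with one that requires data through the 60-month post-RT visit, including its window of plus or minus 1 month.
2. In Section 18.1, add month 54 to the event-monitoring column heading so that it matches footnote 3.

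The cost is wording only, because the visit is already scheduled. Required follow-up lengthens by at most about 97 days per man, which is the late edge of the 60-month window.

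The change puts men in the risk set at 60 months from registration and covers the gap for deaths and diagnosed clinical recurrences. It does not recover PSA failures that arise between the month-54 visit and 60 months from registration, and the report of 5-year DFS should say so.

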16.3.2.5 A late adverse event is defined as an adverse event that occurs any time between 3 months and 2 years after completion of proton beam therapy. The rate of \geq grade 2 GI or GU late adverse events will be estimated by the number of patients with a \geq grade 2 GI or GU late adverse event divided by the total number of evaluable patients. Exact binomial 95% confidence intervals for the true rate of \geq grade 2 GI or GU late adverse events will be calculated.

16.3.2.6 Adverse Events: All eligible patients that have initiated treatment will be considered evaluable for assessing adverse event rate(s). The maximum grade for each type of adverse event will be recorded for each patient, and frequency tables will be reviewed to determine patterns. Additionally, the relationship of the adverse event(s) to the study treatment will be taken into consideration. Acute and late adverse events (as defined in sections 16.3.2.2 and 16.3.2.3) will be summarized separately.

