16.3.3 Correlative Analyses

16.3.3.1 Patients will complete the Expanded Prostate Cancer Index Composite short form (EPIC-26) questionnaire at baseline and at the specified post-treatment time points as shown Section 4.0. Subdomains for urinary, bowel, and sexual function will be evaluated at each time point and summarized descriptively. Changes across time will be evaluated to assess patient function and quality of life after study treatment.

16.3.4 Over Accrual: If more than the target number of patients are accrued, the additional patients will not be used to evaluate the stopping rule or used in any decision making processes; however, they will be included in final endpoint estimates and confidence intervals.

16.4 Data & Safety Monitoring:

16.4.1 The principle investigator(s) and the study statistician will review the study at least twice a year to identify accrual, adverse event, and any endpoint problems that might be developing. The Mayo Clinic Radiation Oncology Data Safety Monitoring Board (DSMB) is responsible for reviewing accrual and safety data for this trial at least once a year, based on reports provided by the statistical office.

16.4.2 Adverse Event Stopping Rules: The stopping rules specified below are based on the knowledge available at study development. We note that the Adverse Event Stopping Rule may be adjusted at any time during the conduct of the trial and in consideration of newly acquired information regarding the adverse event profile of the treatment(s) under investigation. The study team may choose to suspend accrual if there are unexpected adverse event profiles that have not crossed the specified rule below.

Accrual will be temporarily suspended, if at any time we observe events considered at least possibly related to study treatment (i.e. an adverse event with attribute specified as “possible,” “probable,” or “definite”) that satisfy one of the following:

- If 4 or more patients in the first 20 treated patients experience a grade 3 or higher GI or GU adverse event at least possibly related to treatment at any time and after 3 months following completion of the protocol treatment
- After the first 20 patients have been treated: if $\geq 20\%$ of all patients experience a grade 3 or higher GI or GU adverse event at least possibly related to treatment at any time after 3 months following the completion of protocol treatment.

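### Section 13.1 ends follow-up of patients who started treatment and stopped for reasons other than toxicity or progression, although the analysis plan counts them

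*Combined protocol and SAP*

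**What the plan says.** Section 13.1 applies to a patient who "fails to complete the entire course of treatment for reasons other than toxicity or prostate cancer progression". He is inevaluable and is replaced. His baseline characteristics are kept, and then: "However, no further data collection will be collected".

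The neighbouring categories are handled differently:

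- **13.3 (cancel)** covers a patient "if he is removed from the study for any reason before any study treatment is given". Since untreated patients have their own category, 13.1 is left with men who have started treatment.
- **13.2 (ineligible)**: if the patient was treated, "collection of follow-up data will continue in accordance to Section 4.0".
- **13.4 (major violation)**: "The patient will continue the active monitoring phase and the event-monitoring phase of the study".

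Other sections count treated patients and make no exception for 13.1:

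- **16.1.1 and 16.3.1.1** make eligible, consented patients who began treatment evaluable for the primary endpoint. The only exception is major violations.
- **16.3.2.6** makes every eligible patient who started treatment evaluable for adverse event rates.
- **10.4.1.1.1** requires a report of "Any death within 30 days of the patient's last study treatment or procedure regardless of attribution to radiation treatment". 10.4.1.1.2 adds later deaths that are at least possibly related to radiation.
- **16.4.2** suspends accrual on this condition, among others: "If 4 or more patients in the first 20 treated patients experience a grade 3 or higher GI or GU adverse event", restricted to events at least possibly related to treatment and arising more than 3 months after it. Beyond 20 patients the trigger is 20% of all patients.

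**The concern.** The primary endpoint is late grade 3 or higher GI or GU toxicity between 3 months and 2 years after proton therapy. A man who leaves partway through the course has been irradiated and can still develop late injury, whatever his reason for leaving. Section 13.1 nevertheless ends scheduled observation of him, while a treated man who was never eligible, or whose treatment severely violated the protocol, is followed to the end. The documents give no reason for the difference. Replacing a patient in the 51-patient decision does not require ceasing to observe him.

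Three things are at stake. The late-toxicity rate and the adverse event tables have a denominator that includes men with no late data. Disease-free, disease-specific and overall survival lose information on them. The stated reason for leaving also cannot be checked against what happens later, so a man whose preference to stop reflected early symptoms could not be recognised as such.

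**Working it through.** **Step 1. Put the rules side by side.**

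| Patient who has started treatment | Follow-up | In the 16.1.1 evaluable set? | In the 16.3.2.6 set? |
|---|---|---|---|
| Ineligible (13.2) | Continues | No | No |
| Major violation (13.4) | Continues | No | Yes, if eligible |
| Eligible, stops for another reason (13.1) | Ends | Yes, though 13.1 calls him inevaluable | Yes |

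The group that the analysis sets include is the one whose follow-up ends. The contradiction is textual and needs no arithmetic. A death from an unrelated cause during treatment shows it sharply: it is a non-completion for a reason other than toxicity or progression, so 13.1 stops collection, yet 10.4.1.1.1 requires the report.

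**Step 2. Reproduce the plan's own figures.** Inputs are 51 evaluable patients and a promising result with 4 or fewer events (16.2.1.1). The formula is P(X ≤ 4) for X ~ Binomial(51, p).

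| True rate p | 0.20 | 0.15 | 0.10 | 0.05 |
|---|---|---|---|---|
| Stated in 16.2.4 | 0.02 | 0.10 | 0.41 | 0.89 |
| Exact | 0.0159 | 0.1022 | 0.4131 | 0.8896 |

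All four agree at the printed precision.

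**Step 3. Choose a range for k**, the number of treated men whose follow-up 13.1 ends. The documents give no rate. Section 16.2.2 allows 5 of 56 for all losses together: 5/56 = 8.9%, or 20 × 5/56 = 1.8 per 20. I take k = 1 to 3 as an assumption. For the first 20, k = 3 is 3/20 = 15%, above that whole allowance, so it is a high value there.

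**Step 4. Stopping rule, first 20 treated.** If the k men remain in the 20 and cannot add a late event, the chance of triggering is P(Y ≥ 4) with Y ~ Binomial(20 − k, p).

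| k | Trigger among observed | p = 0.20 | p = 0.30 |
|---|---|---|---|
| 0 | 4/20 = 20.0% | 0.589 | 0.893 |
| 1 | 4/19 = 21.1% | 0.545 | 0.867 |
| 2 | 4/18 = 22.2% | 0.499 | 0.835 |
| 3 | 4/17 = 23.5% | 0.451 | 0.798 |

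With 56 treated, the 20% rule needs 12 events (0.20 × 56 = 11.2). At p = 0.20 the chance of reaching 12 is 0.447 for k = 0 and 0.394 for k = 2.

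**Step 5. Primary decision.** Section 16.3.1.2 divides patients with an event by evaluable patients, so a man without data counts as event-free if 16.1.1 governs. The chance of declaring the regimen promising is then P(X ≤ 4) with X ~ Binomial(51 − k, p). At p = 0.15 it is 0.102, 0.112, 0.123 and 0.134 for k = 0, 1, 2 and 3.

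Steps 4 and 5 assume that the unfollowed men have the same event risk as the others. A partial dose could make it lower.

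**The case against.** The strongest reply is that the sentence does less harm than it appears to. Much of this stands.

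- **A reader might infer that deaths and toxicity in these men are never recorded.** The documents do not support that. Section 13.1 bars further collection and does not discard what has been entered. Toxicity is graded weekly during RT (Section 4.0), with forms due at each evaluation (18.1). Serious events (10.3) and deaths (10.4.1) have their own reporting duties, with no exemption for inevaluable patients. What is lost is scheduled follow-up, and unscheduled reporting is a weak substitute for it.
- **A reader might infer that the stopping rule is necessarily diluted.** That holds only if a replaced, inevaluable man stays in the 16.4.2 counts. The wording there points that way, but no section says whether he stays or leaves. If he leaves, the effect in step 4 disappears. Section 16.4.2 also lets the team suspend accrual before a boundary is crossed.
- **A reader might infer that nearly the full late risk goes unobserved**, because the protocol's BED formula gives 24 × 2.7 × 1.9 = 123.1 after 24 fractions against 128.3 for the full course. At a fixed dose per fraction this ratio is simply 24/25 = 96%, and 5 fractions would give 20%. The late stopper is the extreme case, and the documents give no curve from BED to risk.
- **The group is small.** Men who stop for toxicity or progression are not covered by 13.1, and the proton course lasts 5 weeks. On the other side, 13.1 does not limit treatment to RT, and Section 7.0 includes androgen deprivation in protocol treatment, so a literal reading could widen the group.

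None of this reconciles 13.1 with 16.1.1, 16.3.1.1, 16.3.2.6 or 10.4.1.

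**Conclusion.** The point holds as an internal contradiction with a limited, permissive effect. Section 13.1 ends follow-up of eligible men whom the analysis plan counts, and it is out of line with 13.2 and 13.4. The certain consequence, if it is followed as written, is the loss of scheduled late-toxicity and survival data on them.

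The numerical consequence is conditional on three things: the men stay in the denominators as event-free, they number 1 to 3, and they carry the same risk as the others. The chance of stopping at a true rate of 20% then drops by 0.044 to 0.138 (0.589 to 0.545 or 0.451). The chance of wrongly declaring the regimen promising at 15% rises by 0.010 to 0.032 (0.102 to 0.112 or 0.134). Both shifts favour the regimen. The change should be made because it is cheap and concerns the primary endpoint; the design does not fail without it.

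**What to change.** Replace the last sentence of 13.1 with wording such as:

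> Any patient who received at least one proton fraction remains in active and event monitoring per Section 4.0 for adverse events, recurrence and survival, unless he withdraws consent or revokes authorization, and is included in 16.3.2.6 and 16.4.2.

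The exception is needed because 18.2.1 restricts what may be collected after authorization is revoked.

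Two further edits belong with it:

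1. Reconcile the inevaluable-and-replaced rule in 13.1 with the evaluable set in 16.1.1 and 16.3.1.1, so that one rule states whether these men count among the 51. Either add them to the exceptions in 16.1.1 and 16.3.1.1 and report their events separately, or drop the replacement and count them.
2. State whether treatment in 13.1 means proton therapy alone or also androgen deprivation.

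The cost is slightly more data entry for a few patients. The forms already exist (18.1), and the visits and tests are routine care (19.2). Some of these men may decline, so follow-up will not be complete. Sample size and decision thresholds need not change.
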